##### **Handling of ECGs Measured in Triplicate**

If ECG is collected in triplicates, the following approach will be taken.

First, any derivation of ECG parameters will be done before handling ECG triplicates. Next, the mean of the triplicate ECG values will be calculated for each individual ECG parameter, without rounding the result. These calculated means will constitute the analysis values; any derivation (e.g. change from baseline, assignment of abnormalities) and statistic will be based on the mean value of the triplicates.

The values of the original members of a triplicate will be listed.

#### **6.3.3.3.     *Abnormalities***

The actual analysis values and changes from baseline of the QT and QTcF parameters will be categorized into the abnormality classes as defined in the SAP [Appendix II](#).

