8.5.2. Clinical Laboratory Evaluations

The following clinical laboratory tests will be performed:

- **Hematology:** hematocrit, mean corpuscular volume (MCV), mean corpuscular hemoglobin (MCH), mean corpuscular hemoglobin concentration (MCHC), hemoglobin, red blood cell count, red blood cell distribution width, white blood cell count, white blood cell differential count (absolute and relative), platelets, and erythrocyte sedimentation rate (erythrocyte sedimentation rate at screening only).

– **Coagulation:**

INR (only when increase in LFTs, see Section 6.4), activated partial thromboplastin time, and prothrombin time.

– **Clinical chemistry:**

fasting glucose (at baseline [Visit 1], Day 15 [Visit 3], and Day 43 [Visit 5] and the ED visit, if applicable), glycosylated hemoglobin (HbA1c), fasting insulin (at baseline [Visit 1], Day 15 [Visit 3], and Day 43 [Visit 5] and the ED visit, if applicable), homeostatic model assessment of insulin resistance (HOMA IR) (at baseline [Visit 1], Day 15 [Visit 3], and Day 43 [Visit 5] and the ED visit, if applicable), urea, creatinine, creatinine clearance (ClCr), uric acid, sodium, potassium, calcium (total), reflex calcium (free/ionized; only if serum calcium total is elevated), chloride, phosphorus/phosphate, AST, ALT, GGT, total bilirubin, alkaline phosphatase (alkaline phosphatase bone fractions only if alkaline phosphatase is elevated), lactate dehydrogenase, creatine phosphokinase (CK), albumin, total proteins, triglycerides, total cholesterol, high density lipoprotein cholesterol, low density lipoprotein cholesterol, lipase, amylase, high sensitivity CRP, high sensitivity Troponin I and Troponin T (Troponin I on Day 1, later during the study only when troponin T is elevated).

Homeostatic model assessment of insulin resistance (HOMA-IR, see Definition of Terms) and HDL/LDL ratio will be derived from clinical chemistry parameters. An estimate of the creatinine clearance (ClCr) based on the serum creatinine level will be calculated by the central laboratory using the Cockcroft-Gault formula (see Definition of Terms).

– **Urinalysis:**

Dipstick: pH, glucose, proteins (qualitative), blood, leukocytes, ketones.

Microscopic examination of the sediment for cellular elements (cylinders, erythrocytes, leukocytes), if indicated (when the test strip was positive for blood and/or proteins).

Quantitative urine proteins, only when the test strip was positive for proteins.

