#### **6.3.2.2. Derivation Rules**

##### **Derived Laboratory Tests**

Not applicable.

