### **Treatment-Emergent Abnormalities**

Actual value: An abnormal post-baseline abnormality is defined as treatment-emergent when the abnormality is worse compared to the abnormality at baseline or when there is a change in direction (from H to L or from L to H). When the baseline value is missing, post-baseline abnormalities are considered as treatment-emergent.

An abnormal category for change from baseline is always treatment-emergent.

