**Table 1**    **Gradings for Hematology Parameters**

Parameter	L1	L2	L3	L4	H1	H2	H3	H4
Hemoglobin	<LLN	<10 g/dL; <6.2 mmol/L	<8 g/dL; <4.9 mmol/L	NA	>ULN	Increase in >2 g/dL above ULN	Increase in >4 g/dL above ULN	NA
Hematocrit	<LLN	NA	NA	NA	>ULN	NA	NA	NA
Mean corpuscular volume (MCV), mean corpuscular hemoglobin (MCH), mean corpuscular hemoglobin concentration (MCHC)	<LLN	NA	NA	NA	>ULN	NA	NA	NA
Platelet count - (assuming no platelet cluster)	<LLN	<75 x 10  /L	<50 x 10  /L	<25 x 10  /L	>ULN	>600 x 10  /L	>1000 x 10  /L	NA
Leukocytes	<LLN	<3.0 x 10  /L	<2.0 x 10  /L	<1.0 x 10  /L	>ULN	>20.0 x 10  /L	>100.0 x 10  /L	NA
% Polymorphonuclear Leukocytes + Band Cells	NA	NA	NA	NA	>ULN	≥90%	>95%	NA

Parameter	L1	L2	L3	L4	H1	H2	H3	H4
Neutrophils	<LLN	<1.5 x 10  /L	<1.0 x 10  /L	<0.5 x 10  /L	NA	NA	NA	NA
Eosinophils	NA	NA	NA	NA	>ULN	>5.0 x 10  or eosinophils >5%	NA	NA
Lymphocytes	<LLN	<0.8 x 10  /L	<0.5 x 10  /L	<0.2 x 10  /L	>ULN	>4.0 x 10  /L	>20.0 x 10  /L	NA
Red blood cells	<LLN	NA	NA	NA	>ULN	NA	NA	NA

**Table 2** Gradings for Blood Chemistry Parameters

Parameter	L1	L2	L3	L4	H1	H2	H3	H4
Alanine aminotransferase (ALT)	NA	NA	NA	NA	>ULN	>3.0 x ULN	>5.0 x ULN	>8.0 x ULN
Aspartate aminotransferase (AST)	NA	NA	NA	NA	>ULN	>3.0 x ULN	>5.0 x ULN	>8.0 x ULN

Parameter	L1	L2	L3	L4	H1	H2	H3	H4
Gamma-glutamyl transferase (GGT)	NA	NA	NA	NA	>ULN	>2.5 x ULN	>5.0 x ULN	>20.0 x ULN
Alkaline Phosphatase (total)	NA	NA	NA	NA	>ULN	>2.5 x ULN	>5.0 x ULN	>20.0 x ULN
Lactate dehydrogenase (LDH)	NA	NA	NA	NA	>ULN	NA	NA	NA
Total bilirubin	NA	NA	NA	NA	>ULN	>1.5 x ULN	>3.0 x ULN	>10.0 x ULN
Amylase	NA	NA	NA	NA	>ULN	>1.5x ULN	>2.0 x ULN	>5.0 x ULN
Lipase	NA	NA	NA	NA	>ULN	>1.5x ULN	>2.0 x ULN	>5.0 x ULN
Total protein	<LLN	<5.5 g/dL	<5.0 g/dL	NA	NA	NA	NA	NA
C-reactive protein (CRP)	NA	NA	NA	NA	>5mg/L	>10mg/L	>20mg/L	>30mg/L
Activated partial thromboplastin time (APTT)	NA	NA	NA	NA	>ULN	>1.5 x ULN	>2.5 x ULN	NA
Prothrombin time (PT)	NA	NA	NA	NA	≥1.10 x ULN	≥1.25 x ULN	≥1.50 x ULN	≥3.00 x ULN
International normalized ratio (INR)	NA	NA	NA	NA	≥1.2 x Baseline	≥1.5 x Baseline	≥2.5 x Baseline	NA
Creatinine	NA	NA	NA	NA	>ULN	>1.5 x ULN	>3.0 x ULN	>6.0 x ULN

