Glucose (fasting)	<LLN	<55 mg/dL; <3.0 mmol/L	<40 mg/dL; <2.2 mmol/L	<30 mg/dL; <1.7 mmol/L	>ULN	>125 mg/dL; ≥6.95 mmol/L	>250 mg/dL; ≥13.89 mmol/L	≥500 mg/dL; ≥27.75 mmol/L

Parameter	L1	L2	L3	L4	H1	H2	H3	H4
Glucose ( non-fasting )	<LLN	<55 mg/dL; <3.0 mmol/L	<40 mg/dL; <2.2 mmol/L	<30 mg/dL; <1.7 mmol/L	>ULN	>160 mg/dL; ≥8.89 mmol/ L	>250 mg/dL; ≥13.89 mmol/ L	≥500 mg/dL; ≥27.75 mmol/L
HbA1c	NA	NA	NA	NA	> 6.0 %	> 6.5 %	NA	NA
Fasting insulin	<2.6 μU/mL or 18.1 pmol/L	NA	NA	NA	>24.9 μU/m or 172.9 pmol/L	NA	NA	NA
Cholesterol	NA	NA	NA	NA	>ULN	>300 mg/dL; ≥7.75 mmol/L	>400 mg/dL ; >10.34 mmol/L	>500 mg/dL; ≥12.92 mmol/L
Low-density lipoprotein (LDL)	NA	NA	NA	NA	NA	≥160 mg/dL; ≥4.12 mmol/ L	≥190 mg/dL; ≥4.90 mmol/ L	NA
High-density lipoprotein (HDL)	NA	<40 mg/dL; <1 mmol/L	NA	NA	NA	NA	NA	NA
Triglycerides	NA	NA	NA	NA	>ULN	>300 mg/dL; ≥3.42 mmol/ L	>500 mg/dL; ≥5.7 mmol/ L	>1,000 mg/d L; ≥11.4 mmol/L
Calcium ( corrected for albumin )	<LLN	<8.0 mg/dL; <2.0 mmol/L	<7.0 mg/dL; <1.75 mmol/L	<6.0 mg/dL; <1.5 mmol/L	>ULN	>11.5 mg/dL ; >2.9 mmol/L	>12.5 mg/dL ; >3.1 mmol/L	>13.5 mg/dL ; >3.4 mmol/L

Parameter	L1	L2	L3	L4	H1	H2	H3	H4
Ionized calcium	<LLN	<1.0 mmol/L	<0.9 mmol/L	<0.8 mmol/L	>ULN	>1.5 mmol/L	>1.6 mmol/L	>1.8 mmol/L
Sodium	<LLN	<130 mEq/L; <130 mmol/L	<125 mEq/L; <125 mmol/L	<120 mEq/L; <120 mmol/L	>ULN	>150 mEq/L; >150 mmol/L	>155 mEq/L; >155 mmol/L	>160 mEq/L; >160 mmol/L
Chloride	<LLN	NA	NA	NA	>ULN	NA	NA	NA
Potassium	<LLN	NA	<3.0 mmol/L	<2.5 mmol/L	>ULN	>5.5 mmol/L	>6.0 mmol/L	>7.0 mmol/L
Phosphate	<LLN	<2.0 mg/dL; <0.65 mmol/L	<1.4 mg/dL; <0.45 mmol/L	<1.0 mg/dL; <0.32 mmol/L	>ULN	NA	NA	NA
Creatine phosphokinase (CPK)	NA	NA	NA	NA	> ULN	>2.5 x ULN	>5 x ULN	>10 x ULN
Uric acid	NA	NA	NA	NA	>ULN	≥10 mg/dL; ≥0.59 mmol/L	≥12 mg/dL; ≥0.71 mmol/L	≥15 mg/dL; ≥0.89 mmol/L
Albumin	<LLN	<30 g/L	<20 g/L	NA	NA	NA	NA	NA
eGFR (or Cr/Cl)	<LLN	<60 ml/min/ 1.73 m 	<30 ml/min/ 1.73 m 	<15 ml/min/ 1.73 m 	NA	NA	NA	NA
Blood urea nitrogen (BUN)	NA	NA	NA	NA	>ULN	>2.5 ULN	>5 ULN	>10 ULN
25-hydroxyvitamin D	< 20 ng/mL or < 50 nmol/mL	NA	NA		> 60 ng/mL or > 125 nmol/mL	NA	NA	NA

Parameter	L1	L2	L3	L4	H1	H2	H3	H4
PTH (0-20y)	<9 pg/mL or 1 pmol/L	NA	NA	NA	> 52 pg/mL or 5.5 pmol/L	NA	NA	NA
PTH (>20y)	<10 pg/mL or 1.1 pmol/L	NA	NA	NA	> 65 pg/mL or 6.9 pmol/L	NA	NA	NA
TRAP5b	<LLN	NA	NA	NA	>ULN	NA	NA	NA
P1NP	<LLN	NA	NA	NA	>ULN	NA	NA	NA
CTX Type I Collagen (20y - 51y), female	NA	NA	NA	NA	>574 pg/mL	NA	NA	NA

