CTX Type I Collagen (20y - 30y) male	NA	NA	NA	NA	> 677 pg/mL	NA	NA	NA
CTX Type I Collagen (30y - 51y) male	NA	NA	NA	NA	> 685 pg/mL	NA	NA	NA
CTX Type I Collagen (> 51y) female	NA	NA	NA	NA	> 1009 pg/mL	NA	NA	NA
CTX Type I Collagen (51y - 71y) male	NA	NA	NA	NA	> 705 pg/mL	NA	NA	NA

Parameter	L1	L2	L3	L4	H1	H2	H3	H4
CTX Type I Collagen (>71y) male	NA	NA	NA	NA	> 855 pg/mL	NA	NA	NA

**Table 3** Gradings for Urine Analysis Parameters

Parameter	L1	L2	L3	L4	H1	H2	H3	H4
Urine erythrocytes	NA	NA	NA	NA	≥ULN	≥10 cells/HPF	NA	NA
Urine protein	NA	NA	NA	NA	1+ proteinuria	2+ and 3+ proteinuria; urinary protein <3.5 g/24 hrs	urinary protein ≥3.5 g/24 hrs; 4+ proteinuria	NA
Urine glucose	NA	NA	NA	NA	>ULN (presence of glucose)	NA	NA	NA

LLN: lower limit of normal, ULN: upper limit of normal, NA: not applicable.

Any laboratory parameter with treatment-emergent (i.e., worsening from baseline) abnormalities of grade 2 or above (ie, H2/L2 or higher/lower) should be considered a 'marked laboratory abnormality'. Marked laboratory abnormalities should be described in a corresponding section of the CSR as per ICH E3 guidance, section 12.4.2.3.

**APPENDIX II: Vital Signs and Electrocardiogram grading****Table 4 Gradings for Vital Signs and Electrocardiogram Parameters**

Parameter	L1	L2	L3	L4	H1	H2	H3	H4
Systolic blood pressure (mmHg)	<90	<60	NA	NA	NA	≥140	≥160	≥180
Diastolic blood pressure (mmHg)	<60	<45	NA	NA	NA	≥90	≥100	≥120
Heart rate (bpm)	<60	<50	<40	NA	>100	>115	>130	NA
Body temperature (°C)	NA	<35	NA	NA	>38	NA	NA	NA
Respiratory rate (breaths per minute)	<12	NA	NA	NA	>20	NA	NA	NA
O 2 saturation (%)	<95	<90	NA	NA	NA	NA	NA	NA
Weight	≥7% decrease from baseline	NA	NA	NA	≥7% increase from baseline	NA	NA	NA
QTc interval on ECG (ms)	NA	NA	NA	NA	>450	>480	>500	NA
QTc change from baseline (ms)	NA	NA	NA	NA	NA	>30	>60	NA
PR interval on ECG (ms)	<110	NA	NA	NA	>200	NA	NA	NA

Parameter	L1	L2	L3	L4	H1	H2	H3	H4
QRS complex on ECG (ms)	<60	NA	NA	NA	>120	NA	NA	NA

Source: FRM-MED-005/006, valid on 08JUL2020.

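### Three SAP safety-grading rules do not work as written: uncorrected QT has no limits to be classed by, serum calcium is graded on an albumin-corrected scale that neither document derives, and INR is graded against a baseline that is not scheduled

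*SAP*

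**What the plan says.** **ECG.** SAP 6.3.3.1 lists heart rate, RR, PR, QRS, uncorrected QT and QTcF as analysed parameters. For abnormality classes, SAP 6.3.3.3 reads: "The actual analysis values and changes from baseline of the QT and QTcF parameters will be categorized into the abnormality classes" of Appendix II. The worst-case rule in the same section also covers only QT and QTcF and selects the highest value. The treatment-emergent rule adds a second trigger: "when there is a change in direction (from H to L or from L to H". Protocol 9.3.5.6 plans frequency analyses of ECG abnormalities, on values and on changes, without restricting them to QT.

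**Calcium.** SAP 6.3.2.3 takes toxicity grades from Appendix I. The serum calcium row there is marked "corrected for albumin", and there is a separate row for ionized calcium. Protocol 8.5.2 lists "calcium (total), reflex calcium (free/ionized; only if serum calcium total is elevated", and lists albumin as well. In SAP 6.3.2.2, the entry under "Derived Laboratory Tests" is not applicable.

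**INR.** Appendix I grades INR at 1.2, 1.5 and 2.5 times baseline (H1 to H3). Protocol 8.5.2 lists "INR (only when increase in LFTs, see Section 6.4". SAP 4.3.4 defines baseline as the last assessment before first intake.

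**The concern.** A grading rule needs a measured or derived value and a limit for that value. Each of these three lacks one or the other: uncorrected QT has no limit, corrected calcium has no derived value, and INR has no planned denominator. PR and QRS show the reverse gap: they have data and limits, but no instruction joins them.

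At stake are the graded shift tables and the treatment-emergent frequency tables in SAP 6.3.2.9 and 6.3.3.4. A programmer must either leave these cells empty or improvise, for example by putting QTc limits on raw QT or corrected-calcium limits on total calcium. An improvised choice would be made outside the SAP and could assign the wrong grade.

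**Working it through.** The plan states no figure to reproduce. The check sets the rules against the limits and the data; the numbers after that are illustrations.

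**1. Rules, limits and data**

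| Item | Sent for grading? | Limit in the appendices | Value available? |
|---|---|---|---|
| QTcF | Yes (6.3.3.3) | H1 >450, H2 >480, H3 >500 ms; change H2 >30, H3 >60 ms | Yes |
| Uncorrected QT | Yes (6.3.3.3) | None | Yes |
| PR | No | L1 <110, H1 >200 ms | Yes |
| QRS | No | L1 <60, H1 >120 ms | Yes |
| ECG heart rate | No | L1 to L3 and H1 to H3 | Yes |
| Calcium, albumin-corrected | Yes (6.3.2.3) | L2 <2.0, H2 >2.9 mmol/L, among others | Not derived in either document |
| Ionized calcium | Yes | L1 to L4 and H1 to H4 | Only after a high total |
| INR | Yes | Multiples of baseline | Only after a liver-test increase |

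QTc has no L class, so the H-to-L trigger cannot act on QTcF. The highest-value rule could not select a low PR, QRS or heart rate even if those were added.

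**2. QTc limits placed on raw QT.** QTcF = QT × (1000/RR)^(1/3), as in SAP 6.3.3.2, with RR = 60000/HR in ms. (The SAP's fallback for a missing RR is written differently; that is a separate matter.)

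| QT (ms) | HR (bpm) | Class if QT is used | QTcF (ms) | Class by QTcF |
|---|---|---|---|---|
| 460 | 50 | H1 | 432.9 | none |
| 460 | 75 | H1 | 495.5 | H2 |
| 460 | 100 | H1 | 545.4 | H3 |
| 400 | 100 | none | 474.3 | H1 |

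The error runs in both directions and depends on heart rate.

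**3. Calcium.** The documents give no formula. Assume corrected = total + k × (ref − albumin), with k = 0.02 or 0.025 mmol/L per g/L and ref = 40 or 42 g/L. Take total calcium 1.95 mmol/L, which is L2 if graded uncorrected.

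| Albumin (g/L) | Corrected, range over the four formulas (mmol/L) | Still L2 (<2.0)? |
|---|---|---|
| 28 | 2.19 to 2.30 | No |
| 32 | 2.11 to 2.20 | No |
| 36 | 2.03 to 2.10 | No |
| 40 | 1.95 to 2.00 | Yes in three of four |

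Example: 1.95 + 0.02 × (40 − 28) = 2.19. The ionized reflex does not help here, because it is triggered only by a high total.

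**4. INR.** Take a triggered INR of 1.4 and assume a range of baselines.

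| Assumed baseline | Ratio | Grade |
|---|---|---|
| 0.9 | 1.4/0.9 = 1.556 | H2 |
| 1.0 | 1.400 | H1 |
| 1.1 | 1.273 | H1 |
| 1.2 | 1.167 | none |

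The grade depends on a number the protocol does not plan to collect. SAP 6.3.2.6 says what to do when baseline is missing, but only decides whether an existing post-baseline grade is treatment-emergent. It cannot create the grade.

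**The case against.** The strongest reply is that these are small gaps in a descriptive safety analysis of 30 planned subjects, with other outputs covering the same ground. Much of that stands.

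- **ECG.** QTcF can be fully graded. PR and QRS receive descriptive statistics and plots, and ECG interpretations are tabulated. ECGs are read centrally, and clinically significant findings become adverse events. The heart rate row can serve pulse rate through SAP 6.3.4.3.
- **Calcium.** Tests receive low/normal/high classes with shift tables under SAP 6.3.2.4 and 6.3.2.9. SAP section 1 places technical derivations in a separate document that is not available here, and Appendix I warns that some rows may be for unmeasured tests.
- **INR.** Prothrombin time is not restricted to a liver-test trigger and is graded in multiples of ULN. INR >1.5 with AST or ALT ≥3×ULN is reportable as an SAE.

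These replies do not remove the gaps. Total calcium, PR, QRS and triggered INR are all measured, so the unmeasured-test note does not excuse them. A separate specification that derived corrected calcium would contradict SAP 6.3.2.2.

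The reply does rule out several stronger readings. A reader might infer from the H-to-L wording that PR, QRS and heart rate were clearly meant to be classed. But Appendix II is a sponsor form that also carries respiratory rate and oxygen saturation, which are not analysed here, and the wording matches the laboratory rule, so it may be generic. A reader might also link the missing PR and QRS classes to the conduction-abnormality criterion in protocol 6.4. That criterion rests on CTCAE Grade 3 or clinical significance, while Appendix II gives PR and QRS only L1 and H1, so graded tables could not identify it. Nor is it right that no subject could have a valid calcium grade: reflex ionized calcium is gradable.

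**Conclusion.** The point holds in limited form. Within the ECG section, only uncorrected QT cannot be graded; PR and QRS have limits that the ECG text never calls, although the protocol promises frequency analyses of ECG abnormalities. On these two documents, total calcium has no rule that puts it on the stated scale, and low calcium in particular has no toxicity grade. A triggered INR generally cannot be graded unless a baseline value happens to exist.

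The impact is modest and confined to the descriptive graded safety tables. The documents do not support any inference about subject monitoring, stopping of treatment or the primary endpoint. The illustrations rest on assumed calcium formulas and assumed INR baselines; the gaps themselves do not. The calcium conclusion is conditional on the separate derivation document not supplying a formula.

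**What to change.** 1. **SAP 6.3.3.3, classes.** Drop the classing of uncorrected QT. Apply Appendix II to QTcF, PR, QRS and ECG heart rate.
2. **SAP 6.3.3.3, worst case.** Extend the rule to the low direction, taking the lowest value, for parameters with L limits. Without this, naming PR, QRS and heart rate would still leave low values unselected.
3. **SAP 6.3.2.2.** Replace the not-applicable entry with albumin-corrected calcium, derived from the total calcium and albumin already collected. State the formula, and grade the corrected value by Appendix I.
4. **Appendix I and SAP 6.3.2.8.** Grade INR on a basis that needs no baseline, such as multiples of ULN. Tabulate INR >1.5, the value the protocol already uses as a sign of liver damage.

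The cost is SAP wording and a few table rows. No new data are needed, and the primary analysis is untouched.

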### **Worst-Case Abnormality**

The worst-case post-baseline categorized actual analysis value and the worst-case categorized change from baseline for QT and QTcF will be determined per subject, per parameter, and for each analysis period, using all non-missing post-baseline records (including unscheduled and FU visits).

The worst-case categorized actual analysis value is the category corresponding to the highest post-baseline actual value. In case of several equal highest post-baseline actual values, the earliest occurrence will be taken for the analyses and will be flagged in the listings.

The worst-case change from baseline is the category corresponding to the largest increase (positive change) from baseline. In case of several equal largest increase from baseline, the earliest occurrence will be taken for the analyses and will be flagged in the listings.

### **Treatment-Emergent Abnormalities**

Actual value: An abnormal post-baseline abnormality is defined as treatment-emergent when the abnormality is worse compared to the abnormality at baseline or when there is a change in direction (from H to L or from L to H). When the baseline value is missing, post-baseline abnormalities are considered as treatment-emergent.

An abnormal category for change from baseline is always treatment-emergent.

#### **6.3.3.4. Presentation of Results**

No formal inferential statistics (p-values) will be derived.

Continuous parameters will be summarized by means of descriptive statistics (including 90% CI of the mean change) by parameter, treatment group and analysis window. Actual values, change from baseline and percent changes from baseline will be tabulated separately.

Profile line plots by subject of all actual observed values using relative day (ADY) will be presented by treatment group. Graphs of the mean (+- SE) actual values over time and of the mean (+- SE) change from baseline and percent change from baseline will be presented. A line plot by subject of the change from baseline will also be provided by treatment group.

The analysis of abnormalities will focus on assessments reported during the treatment period. Results reported during the screening or post-treatment (if defined) period will only be listed.

Abnormalities of the actual values will be presented as shift tables of the worst-case abnormality versus the baseline abnormality. The table will be created per parameter, treatment group and analysis period.

A frequency table of the number (percent) of subjects with treatment-emergent worst-case abnormalities and the worst change per parameter, treatment group and analysis period will be presented.

A frequency table per treatment group and time point of the ECG interpretations as recorded in the case report form (CRF) will be provided.

A Listing will be provided along with abnormality.

#### **6.3.4. Vital Signs**

##### **6.3.4.1. Available Data**

The following vital signs parameters will be analyzed: weight (kg), BMI (kg/m^2), diastolic and systolic blood pressure (mmHg), pulse rate (beats/min) and body temperature (C).

##### **6.3.4.2. Derivation Rules**

Not applicable.

##### **6.3.4.3. Abnormalities**

Vital signs data will be categorized according to the cutoffs provided in the SAP [Appendix II](#).

##### **6.3.4.4. Treatment-Emergent Principle**

A post-baseline abnormality class L or H is defined as treatment-emergent when it differs from the abnormality class at baseline. If the baseline result is missing, a post-baseline abnormality L or H will be considered as treatment-emergent.

An abnormal category for change from baseline is always treatment-emergent.

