### 6.3.2.6. Treatment-Emergent Principle

#### Toxicity Grades

A post-baseline toxicity grade 1, 2, 3 or 4 is defined as treatment-emergent when higher than the toxicity grade of the baseline result or when there is a change in direction (from H to L or from L to H). If the baseline result is missing, a post-baseline toxicity grade 1, 2, 3 or 4 will be considered as treatment-emergent.

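### The vital-sign treatment-emergent rule compares classes although the data are graded, so it either misses same-direction worsening of pulse and blood pressure or flags improvements

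*SAP*

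**What the plan says.** SAP 6.3.4.3 states: "Vital signs data will be categorized according to the cutoffs provided in the SAP" Appendix II. The table there is headed "Gradings for Vital Signs and Electrocardiogram Parameters" and has columns L1 to L4 and H1 to H4. Its heart-rate row reads "Heart rate (bpm) <60 <50 <40 NA >100 >115 >130 NA". Systolic pressure has L1 <90, L2 <60, H2 ≥140, H3 ≥160 and H4 ≥180. Diastolic pressure has L1 <60, L2 <45, H2 ≥90, H3 ≥100 and H4 ≥120.

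SAP 6.3.4.4 defines treatment-emergent for these data: "A post-baseline abnormality class L or H is defined as treatment-emergent when it differs from the abnormality class at baseline". Two further clauses follow: "If the baseline result is missing, a post-baseline abnormality L or H will be considered as treatment-emergent" and "An abnormal category for change from baseline is always treatment-emergent".

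The SAP uses a different rule for other graded data. In SAP 6.3.2.6 a laboratory toxicity grade "is defined as treatment-emergent when higher than the toxicity grade of the baseline result", or when the direction changes. In SAP 6.3.3.3 an ECG abnormality "is defined as treatment-emergent when the abnormality is worse compared to the abnormality at baseline", or when the direction changes. The ECG grades come from the same Appendix II table. The vital-sign sentence nearly repeats the other rule in SAP 6.3.2.6, which covers laboratory results that have no grades.

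The flag feeds the last vital-sign table in SAP 6.3.4.6, which counts subjects whose worst-case abnormality is treatment-emergent. The worst case is the category of the highest post-baseline value.

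**The concern.** A rule built for three categories (low, normal, high) has been applied to data with up to three grades in each direction. For ungraded results, a change of class is the only change that can be seen. For graded results it discards the grade and so ignores worsening in subjects who enter already outside the normal band.

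Such subjects can enrol. Inclusion criterion 6 admits abnormalities that fit the disease or that the investigator judges not clinically significant. The eligibility criteria shown set no numeric limit on blood pressure or on low pulse.

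At stake is the accuracy of one safety table in a small study. With 20 subjects planned on drug and 10 on placebo, one subject moves a percentage by 1/20 = 5 points or 1/10 = 10 points. The rule also departs from the SAP's general use of the term: SAP 6.3.1.1 counts worsening adverse events as treatment-emergent, and the note to Appendix I equates treatment-emergent with worsening from baseline.

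**Working it through.** The plan gives no figure to reproduce. The check applies the written rule to the Appendix II cutoffs. Using the heart-rate row for pulse is an assumption: SAP 6.3.4.1 lists pulse rate, and Appendix II has no separate pulse row.

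**Step 1: single cases under three rules.** Rule A is 6.3.4.4 with *class* meaning L or H. Rule B is the same sentence with *class* meaning the grade. Rule C is the ECG-type rule (worse grade, or change of direction).

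| Case | Grades | A | B | C |
|---|---|---|---|---|
| Pulse 58 to 38 | L1 to L3 | no | yes | yes |
| Systolic 142 to 182 | H2 to H4 | no | yes | yes |
| Diastolic 92 to 121 | H2 to H4 | no | yes | yes |
| Systolic 182 to 142 | H4 to H2 | no | yes | no |
| Pulse 70 to 38 | normal to L3 | yes | yes | yes |

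Rule A misses three worsenings. Rule B catches them but flags the improvement in row four. Only rule C classifies all five correctly.

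**Step 2: all worsening transitions.** Count every move to a worse grade, from normal to abnormal, or from one direction to the other.

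- Pulse (3 low and 3 high grades): 6 from normal + 3×3 low to high + 3×3 high to low + 3 within low + 3 within high = 30. Rule A misses the 3 + 3 = 6 within a direction.
- Systolic (2 low, 3 high): 5 + 6 + 6 + 1 + 3 = 21. Rule A misses 1 + 3 = 4.
- Diastolic (2 low, 3 high): 21 in the same way, 4 missed.
- Temperature (1 low, 1 high): 2 + 1 + 1 = 4, none missed.

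Total missed: 6 + 4 + 4 = 14. Reversing each of these gives an improvement between two abnormal grades, so rule B wrongly flags 14 improvements.

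**Step 3: do the other clauses help?** The missing-baseline clause does not apply when a baseline exists. The change-from-baseline clause needs a change category, and among the analysed vital signs Appendix II gives one only for weight (7% either way). Pulse and blood pressure gain nothing.

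**Step 4: interaction with the worst case.** Take pulse 58 at baseline, then 38 and 62. The highest post-baseline value is 62, which is normal, so no rule for 6.3.4.4 can count the 38. With the highest value as worst case, a baseline of L1 can register as worse in the low direction only if every post-baseline reading is below 50. Correcting 6.3.4.4 alone therefore repairs the high direction but leaves most low-direction worsening uncounted.

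**The case against.** The strongest reply is that little is lost. The treatment-emergent table is one of several vital-sign outputs, listed after descriptive statistics, graphs of means and shift tables. If the shift table shows grades, systolic 142 to 182 appears there as H2 to H4, because 182 is the highest value. Protocol 8.5.4 has clinically significant abnormal values recorded as adverse events, and worsening adverse events count as treatment-emergent. Safety is analysed descriptively, and neither the primary endpoint nor the signal-detection result uses this flag. The word *class* is also ambiguous: SAP 6.3.3.3 uses it for the graded Appendix II categories, and on that reading the examples of worsening are counted.

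Much of this stands and limits the point. A reader might infer that such deterioration is never counted anywhere, or that the affected table is the main vital-sign safety summary. The documents support neither: the omission concerns the flag and its frequency table under the L-or-H reading, and no document ranks the table.

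The reply does not rescue the sentence. The grade reading replaces missed worsening with flagged improvement, so the rule is wrong either way. The shift table helps only in the high direction and only if it displays grades, which the SAP does not say. The adverse-event route depends on the investigator's judgement of each value.

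**Conclusion.** The rule in SAP 6.3.4.4 does not suit graded data and disagrees with the SAP's own rules for laboratory grades and ECG. Under the L-or-H reading it leaves 14 same-direction worsening transitions for pulse and blood pressure out of the treatment-emergent table; under the grade reading it admits improvements. Temperature (one grade per direction) and weight (graded by change) are unaffected, and BMI has no cutoffs.

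The number of subjects affected cannot be found in the documents, which give no baseline distribution of vital signs. For illustration only: if 10% to 25% entered with pulse below 60, then 0.10×20 = 2 to 0.25×20 = 5 subjects on drug could not contribute a treatment-emergent low pulse under the L-or-H reading. That is a count of subjects the rule cannot flag in that direction, not a forecast of how many would worsen.

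The conclusion rests on the wording of 6.3.4.4 and, for pulse only, on applying the heart-rate row. The point is worth correcting because it affects a safety table, but no efficacy conclusion depends on it.

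**What to change.** Replace the first sentence of SAP 6.3.4.4 with the rule already in SAP 6.3.2.6 for toxicity grades and in SAP 6.3.3.3 for ECG: an abnormality is treatment-emergent when its post-baseline grade is worse than the baseline grade in the same direction, or when the direction changes. Cite the toxicity-grade rule by name, because 6.3.2.6 also contains the class-differs rule for ungraded results. Keep the missing-baseline and change-from-baseline clauses.

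Pair this with a vital-sign worst case determined separately for the low and high directions, as SAP 6.3.2.7 does for laboratory grades. Without it, the highest-value rule would still hide low-direction worsening. State that the shift table displays Appendix II grades and that the heart-rate row applies to pulse.

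The cost is a few sentences of SAP text and a small programming change. No new data are needed and no cutoff changes.
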